2.8.4 Other safety data

2.8.4.1 ECG and cardiac imaging data

ECG abnormality for baseline and any post baseline assessments will be summarized by treatment. A listing of all ECG assessments will be produced by treatment with notable values flagged.

2.8.4.2 Vital signs

Vital sign assessments are performed in order to characterize the basic body function. The following parameters will be collected: height (cm), weight (kg), body temperature (°C), pulse rate (beats per minute), systolic and diastolic blood pressure (mmHg).

Data handling

Vital signs collected on treatment will be summarized. Values measured outside of on-treatment period will be flagged in the listings.

Data analysis

For analysis of vital signs, the clinically notable vital sign criteria are provided in [Table 2-8](#):

Table 2-8 Clinically notable changes in vital signs

Vital sign (unit)	Clinically notable criteria	
	above normal value	below normal value
Weight (kg)	increase > 10% from Baseline	decrease > 10% from Baseline
Systolic blood pressure (mmHg)	>=180 with increase from baseline of >=20	<=90 with decrease from baseline of >=20
Diastolic blood pressure (mmHg)	>=105 with increase from baseline of >=15	<=50 with decrease from baseline of >=15
Pulse rate (bpm)	>=100 with increase from baseline of >25%	<=50 with decrease from baseline of > 25%
Body temperature (°C)	>= 39.1	-

The number and percentage of subjects with notable vital sign values (high/low) will be summarized by treatment.

A listing of all vital sign assessments will be produced by treatment with notable values and assessments, collected outside of on-treatment, flagged.

2.9 Pharmacokinetic endpoints

PAS will be used in the pharmacokinetic data analysis.

PK concentrations

Descriptive statistics (n, m (number of non-zero concentrations), arithmetic mean, CV% mean, SD, median, geometric mean, CV% geo-mean, minimum and maximum) for canakinumab concentration will be presented at each scheduled time point for the PAS.

Individual concentration-time profiles for canakinumab evaluable concentrations with median will be displayed graphically for PAS on the semi-log view. In addition, the mean (+/- SD) and geometric mean concentration-time profiles for canakinumab over time will be displayed graphically for PAS on the linear and semi-log view. Only time points with $n \geq 4$ observations will be shown on the figure.

All individual plasma canakinumab concentration data will be listed by treatment for the FAS.

Handling of PK data below LLOQ or missing

All concentration values below the lower limit of quantitation (LLOQ) are set to zero by the Bioanalyst, and will be displayed in the listings as zero and flagged. LLOQ values will be treated as zero in any calculations of summary statistics, and treated as missing for the calculation of the geometric means and their CV%. The number of non-zero concentrations will also be reported in the summary statistics.

Missing values for any PK data will not be imputed and will be treated as missing.

Population pharmacokinetic analysis

If there is adequate amount of data, a mixed-effects model may be applied to the serum canakinumab concentration-time data from this study to characterize canakinumab exposure and to determine the effects of intrinsic (i.e. demographic factors) and extrinsic covariates (e.g. concomitant medications) on canakinumab exposure. If there is sufficient data for analysis, the details of the population pharmacokinetic analyses may be provided in a separate reporting and analysis plan, and the results may be reported in a separate population pharmacokinetic report.

2.10 PD and PK/PD analyses

2.10.1 Analysis of relationship between canakinumab exposure and efficacy/safety endpoints

2.10.1.1 Evaluable Ctrough concentration

For canakinumab, steady state pre-dose evaluable concentrations (as defined in PAS) collected before dose administration on and after Day 1 of Cycle 6 and beyond are steady state evaluable Ctrough.

2.10.1.2 Average evaluable Ctrough concentration

Average steady state evaluable Ctrough concentration will be used in the exposure/response and exposure/safety analyses. Each subject may have one or more steady state evaluable Ctrough concentration values. The average steady state evaluable Ctrough is defined as:

$C_{min_avg_ss}$ = geometric mean of all steady state *evaluable Ctrough* for each subject, considering the distribution of PK concentration is generally lognormal

Quartile of average trough concentration is defined as:

- <Q1: <25th percentile
- Q1 to <Q2: ≥25th percentile and <50 percentile
- Q2 to <Q3: ≥50th percentile and <75th percentile
- ≥Q3: ≥75th percentile

Subject demographic characteristics will be summarized for all subjects and by quartile of $C_{min_avg_ss}$.

2.10.1.3 Correlations between PK exposure and efficacy measures

Correlations between efficacy endpoints and trough concentrations will be explored using the PAS. Analyses will be focused on the efficacy endpoints: DFS and OS.

The relationship between DFS/OS and PK exposure will be analyzed using Kaplan-Meier methodology.

Steady state evaluable Ctrough concentrations as defined in [Section 2.10.1.2](#) will be included in calculating average steady state trough concentration with the following additional rules:

- for subjects who had a DFS event, only steady state trough concentrations observed on or before the date of DFS event will be included;

- for subjects who did not have a DFS event, all steady state trough concentrations observed on or before the date of last recurrence assessment prior to the cut-off date will be included.

Kaplan-Meier curves for DFS/OS will be fitted for subjects in different quartiles of average steady state evaluable C_{trough} concentration (with above rules applied). DFS/OS will also be summarized by quartiles of average steady state evaluable C_{trough} concentration (with above rules applied).

2.10.1.4 Correlations between PK exposure and safety measures

Correlation between safety endpoints and PK concentrations will be explored using the PAS.

AESI will also be summarized by the quartile of C_{min_avg_ss}, preferred term and maximum CTC grade, for each AESI grouping, as defined in [Section 2.10.1.2](#).

Kaplan-Meier curves for time to onset of grade 2 or worse AESI and time to onset of grade 3 or worse AESI will be fitted for subjects in different quartiles of C_{min_avg_ss} concentration. Time to onset of AESI will also be summarized by quartiles of C_{min_avg_ss}.

2.10.1.6 Immunogenicity

Immunogenicity data will be summarized using the safety set. Immunogenicity will be characterized descriptively by tabulating anti-drug antibodies (ADA) incidence at baseline, ADA incidence on-treatment, treatment induced and treatment boosted ADA. Treatment induced ADA-positive subject is defined as a subject with ADA-negative sample at baseline and at least one treatment-induced ADA-positive sample post baseline. Treatment-boosted ADA-positive subject is defined as a subject with ADA-positive sample at baseline and at least one ADA-positive sample post-baseline with a titer greater than ADA-positive baseline titer by the defined titer fold change.

The ADA-positive NAb samples at baseline and on-treatment will also be summarized. A shift table of subjects with positive or negative anti-canakinumab antibodies overall and by visit will be produced (“positive” corresponds to “worst”). A listing will be provided by subject with supporting information (i.e. ADA sample status at each time point (including titer for positive samples) and subject ADA status). In addition, a listing will also be provided for subjects with neutralizing antibodies (NAB) testing results.

2.11 Patient-reported outcomes

Three patient-reported outcomes (PRO) questionnaires will be assessed: EORTC QLQ-C30, with its QLQ-LC13 lung cancer module, and the EQ-5D-5L. QLQ-C30 and QLQ-LC13 will be considered as the primary scale. Scoring of PRO data and methods for handling of missing items or missing assessments will be handled according to the scoring manual and user guide for each respective patient questionnaire ([Fayers 2001](#), [Van Reenen 2015](#)). No imputation procedures will be applied for missing items or missing assessments.

The FAS will be used for analyzing PRO data. For all PRO analysis, nominal *p*-values will be presented without any statistical inference since there is no adjustment for multiplicity. The baseline is defined as the last PRO assessment on or prior to randomization. In the absence of a better definition

to define clinically relevant changes in this population (lung cancer, adjuvant setting) a 10 point deterioration will be assumed to be clinically meaningful for the QLQ-LC13 and QLQ-C30 (Osoba 1998).

The primary PRO variables of interest are: time to definitive 10 point deterioration symptom scores for each of chest pain, cough and dyspnea per QLQ-LC13 questionnaire

The secondary PRO variables of interest are:

- Utilities derived from the EQ-5D-5L
- Time to first 10 point deterioration symptom scores of pain, cough and dyspnea per QLQ-LC13 questionnaire
- Time to first 10 point deterioration of global health status/QoL, shortness of breath, pain, role functioning, physical functioning and fatigue per QLQ-C30 questionnaire
- Time to 10 point definitive deterioration in global health status/QoL, shortness of breath, pain, role functioning, physical functioning and fatigue per QLQ-C30

The time to 10 point definitive deterioration is defined as the time from the date of randomization to the date of event, which is defined as at least 10 points absolute worsening from baseline of the corresponding scale score, with no later change below this threshold, i.e. <10 points was observed or if this worsening was observed at the last assessment for the subject, or death due to any cause (whichever occurs earlier).

The time to first 10 point deterioration is defined as the time from the date of randomization to the first onset of at least 10 points absolute increase from baseline (worsening) in symptoms scores or at least 10 points absolute decrease from baseline (worsening) in global health status/QoL and functioning scales (role functioning, physical functioning), or death due to any cause, whichever occurs earlier.

If a subject has not had an event, time to definitive deterioration or first deterioration will be censored at the date of the last adequate assessment. If deterioration occurs at the last adequate assessment, this will also be considered definitive. Subjects receiving any further anti-neoplastic therapy related to NSCLC before definitive worsening will be censored at the date of their last assessment before starting this therapy. If a definitive deterioration is observed after two or more missing assessments, subject is censored at the date of their last available questionnaire prior to the deterioration. Subjects with no baseline data will be censored at day 1.

Death is considered as a definitive deterioration event when it occurs within a period of time defined by 2 times the period between two assessments as planned in the study protocol. This avoids overestimating the time to definitive worsening in subjects dying after an irregular assessment scheme. Subjects who die after more than twice the planned period between two assessments since the last assessment are censored at the date of their last available questionnaire.

Censoring reasons for time to definitive deterioration or first deterioration event will be summarized.

All assessments will be included in the time to definitive deterioration or first deterioration analysis. The distribution will be presented descriptively using Kaplan-Meier curves. Summary statistics from Kaplan-Meier distributions will be determined, including the median time to definitive 10 point deterioration along with two-sided 95% confidence interval. Log-rank test stratified by randomization stratification factors will be performed. A Cox regression stratified by randomization stratification factors from IRT will be used to estimate the hazard ratio (HR), along with two-sided 95% confidence interval.

Sensitivity analysis of time to definitive and first deterioration with 5 points will also be performed using the same methodology.

Descriptive statistics will be used to summarize the original scores, as well as change from baseline, of the QLQ-C30, QLQ-LC13, and EQ-5D-5L at each scheduled assessment time point for each treatment arm using time windows as described in [Table 2.1](#). Changes from the baseline by treatment arm at each visit will be plotted for all scales of QLQ-LC13, QLQ-C30 and EQ-5D-5L. Additionally, change from baseline in the scale and subscale values at the time of each assessment will be summarized. Subjects with an evaluable baseline score and at least one evaluable post baseline score during the treatment period will be included in the change from baseline analyses. Tables of compliance and completion rates over time for QLQ-LC13, QLQ-C30 and EQ-5D-5L by treatment arm will be generated.

[figure not shown]
In addition, a repeated measures model for longitudinal data will be used to estimate differences in EORTC QLQ-C30/QLQ-LC13 domains as well as the VAS and utility scores of the EQ-5D-5L between treatment arms. The models will be first based on all assessments. In additional, the models will be repeated to include only assessments collected within 130 days of last study treatment. Any assessments collected after the start of further anti-tumor therapy will not be included in the models.

[figure not shown]
The modeling will mainly be done on the actual score. Note that the modeling of the change in score or the actual score is equivalent since adjustment for baseline score is considered. This repeated measures model will include terms for treatment, the stratification factors, time, and baseline value as main effects, and an interaction term for treatment by time. This analysis will be restricted to subjects with an evaluable baseline score and at least one evaluable post-baseline score. The differences in least square means between the treatment arms and corresponding 95% confidence interval at selected time points will be presented.

Time will be considered as a continuous variable expressed in weeks, i.e. considering that PRO follow a linear trend. As a first approach, an unstructured correlation matrix will be used to model the correlation within subjects. Other structures of the correlation matrix, including AR (1), will be investigated and simplified using likelihood ratio tested if appropriate.

If PRO is found not to follow a linear trend, the time variable might be considered as a categorical variable instead of continuous in the model.

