7.2.6 Patient reported outcomes

7.2.6.1 PRO Questionnaires

The European Organization for Research and Treatment of Cancer's core quality of life questionnaire EORTC-QLQC30 (version 3.0) and it's lung cancer specific module QLQ-LC13 (version 1.0) will be used to collect data on the subject's functioning, disease-related symptoms, health-related quality of life, and health status. The EQ-5D-5L will be used for the purpose of the computation of utilities that can be used in health economic studies. The EORTC QLQ-C30/LC13 as well as the EQ-5D-5L are reliable and valid measures frequently used in clinical

trials of subjects with lung cancer and previously used in the adjuvant setting (Bezjak et al 2008).

The EORTC-QLQC30 is a self-reporting 30-item generic instrument for use in cancer subjects across tumor types including lung cancer. It assesses 15 domains consisting of 5 functional domains (physical, role, emotional, cognitive, social) and 9 symptom domains (fatigue, nausea and vomiting, pain, dyspnea, insomnia, appetite loss, constipation, diarrhea, financial difficulties) and a global health status or HRQoL scale (Aaronson et al 1993). The EORTC QLQ-LC13 complements the QLQ-C30, and measures disease symptoms and treatment-related adverse effects. The lung cancer module incorporates one multi-item scale to assess dyspnea, and 9 single items assessing pain, coughing, sore mouth, dysphagia, peripheral neuropathy, alopecia, and hemoptysis (Bergman et al 1994).

All of the domain scores of the EORTC-QLQC30 and QLQ-LC13 range from 0 to 100. A high score indicates a higher response level. Hence, a high score for a functional scale indicates a high and healthy level of functioning but a high score for a symptom scale indicates a high level of symptoms/problems.

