5.5 Patient reported outcomes: EORTC QLQ-C30/LC13 and EQ-5D-5L/VAS

The text below gives more detailed instructions and rules needed for programming of the analyses described in [Section 2.11](#).

EORTC QLQ-C30 scale scores will be generated by first obtaining the raw scores adding up the item responses on the questions which make up each domain and then applying the linear transformation to the raw scores in accordance with the respective scoring manual provided by the developers. Scores in each scale will be generated if at least half of the items comprising the scale have been answered. For single item scales with missing responses and scales where less than half of the items have not been answered, scale scores will be set to missing.

The scoring approach for the QLQ-LC13 is identical in principle to that for the symptom scales/single items of the QLQ-C30. The dyspnea scale of the QLQ-LC13 is the only multi item scale (all others are single item scales) and should only be used if all items comprising the scale have been answered.

For the calculation of EQ-5D-5L index value, the EQ-5D crosswalk value set for the UK using the time trade-off method will be used. If any one of the five dimensions of health state is missing, the index value will be set to missing.

A repeated measures model for longitudinal data will be used to compare the two treatment arms in terms of the domain scores over time. This longitudinal model will include terms for treatment, the randomization stratification factors, time of visit (duration in days from the time of baseline measurement to the time of a particular post baseline measurement), baseline value as fixed effects, and an interaction term for treatment by time. This analysis will be restricted to subjects with an evaluable baseline score and at least one evaluable post-baseline score. Time will be considered as a continuous variable in this analysis. As a first approach, an unstructured correlation matrix will be used to model the correlation within subjects. Other structures of the correlation matrix, including AR (1), will be investigated and simplified using likelihood ratio tested if appropriate. In particular situations, the non-convergence of the model may be caused by few subjects with assessments at later time points. The possibility of removing few assessments later than a certain time point will be investigated if appropriate.

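### For QLQ-LC13 chest pain and cough, the 5-point sensitivity analysis is identical by construction to the 10-point analysis and cannot show robustness to the threshold

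*SAP*

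**What the plan says.** SAP 2.11 names as primary PRO variables "time to definitive 10 point deterioration symptom scores for each of chest pain, cough and dyspnea per QLQ-LC13 questionnaire". The event is "at least 10 points absolute worsening from baseline of the corresponding scale score", sustained at every later assessment or seen at the last one, or death. The same section concedes that 10 points is adopted for want of a better definition of clinically relevant change in the adjuvant lung cancer setting. The check on that choice is a single sentence: "Sensitivity analysis of time to definitive and first deterioration with 5 points will also be performed using the same methodology".

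Scoring is described in two places. Protocol 7.2.6.1 states: "All of the domain scores of the EORTC-QLQC30 and QLQ-LC13 range from 0 to 100". SAP 5.5 builds the QLQ-C30 scores from raw item responses by "applying the linear transformation to the raw scores in accordance with the respective scoring manual provided by the developers", and adds: "The scoring approach for the QLQ-LC13 is identical in principle to that for the symptom scales/single items of the QLQ-C30". On the structure of the lung module, SAP 5.5 says: "The dyspnea scale of the QLQ-LC13 is the only multi item scale (all others are single item scales"). It allows the dyspnea score only when every dyspnea item is answered. QLQ-C30 scales need only half of their items.

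**The concern.** Lowering a threshold tests something only if some subjects can have a change that meets the lower cut-off and misses the higher one. A single questionnaire item stretched to 0-100 takes few values, so its changes come in large jumps. If no possible change lies from 5 up to, but not including, 10 points, the two analyses are one analysis run twice.

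A reader who sees the same hazard ratio at 5 and at 10 points may conclude that the result does not depend on the threshold. For chest pain and cough, nothing would have been tested. Protocol 10.5.6 leaves the SAP free to specify other definitions of deterioration, and the 5-point repeat is the only one it specifies.

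**Working it through.** The plan gives no event count, power or other figure for this sensitivity analysis, so there is nothing to reproduce first. The check is an enumeration of possible score changes.

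**Inputs**
- Cut-offs of 10 and 5 points, same methodology (SAP 2.11).
- Score range 0 to 100 (Protocol 7.2.6.1); linear transformation of raw scores, and in principle the same for LC13 (SAP 5.5).
- Chest pain and cough are single items; dyspnea has several items, all of which must be answered (SAP 5.5).
- The number of response levels per item and of dyspnea items is in neither document. These are treated as unknown, with ranges.

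**Formula.** For m items of k equally spaced levels, score = (item mean − 1)/(k − 1) × 100. The smallest non-zero change is 100/[m(k − 1)], and every change is a multiple of it.

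**Chest pain and cough (m = 1)**
- k = 4: 100/3 = 33.3
- k = 7: 100/6 = 16.7
- k = 11: 100/10 = 10.0
- k = 12: 100/11 = 9.1, the first k with a change between 5 and 10

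For any k from 2 to 11, a worsening of at least 5 points and one of at least 10 points are the same event: one category or more. The sustained-change rule and the rules for death, missed assessments and new NSCLC therapy do not separate the two analyses, because the cut-off matters only through whether each change reaches it. The identity therefore covers both definitive and first deterioration.

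**Dyspnea (m unknown).** The cut-offs coincide if m(k − 1) is 10 or less.

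| Items × levels (assumed) | m(k − 1) | Step | 5 vs 10 points |
|---|---|---|---|
| 2 × 4 | 6 | 16.7 | same |
| 3 × 4 | 9 | 11.1 | same |
| 4 × 4 | 12 | 8.3 | can differ |
| 5 × 4 | 15 | 6.7 | can differ |
| 3 × 5 | 12 | 8.3 | can differ |

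Protocol 7.2.6.1 does not settle the count. It describes one multi-item dyspnea scale and 9 single items. If the 13 in the module's name is the item total, 13 − 9 = 4 items remain for dyspnea. But it lists only seven single-item symptoms, so that subtraction is not reliable.

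**Confirmation on simulated paths.** The two deterioration rules, without death or censoring, were applied at 5 and 10 points to 20,000 artificial 18-visit paths per structure. Differences: 0 for one four-level item; 0 for three four-level items; 8,389 (definitive) and 14,463 (first) for four four-level items. The last two counts show only that the analyses can separate. They do not predict trial data.

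**The case against.** The strongest reply is that little harm follows. A redundant sensitivity analysis biases no estimate, and identical event counts would be visible in the output. SAP 2.11 presents PRO p-values as nominal and without inference, and Protocol 10.5.6 plans no formal PRO tests. The same domains are also analysed without any threshold, by repeated-measures models and change-from-baseline summaries. All of this stands and limits the importance of the point. It does not restore a threshold check for the two variables.

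A second reply is that a stricter cut-off is demanding. On an assumed four-level item, two categories are 2 × 33.3 = 66.7 points, far above the 10 points that the SAP takes as meaningful. That also stands, and it is why the stricter analysis belongs only among the sensitivity analyses.

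A reader might infer that all three primary PRO variables are affected, or most of the QLQ-C30 scales too. The documents do not support this. Dyspnea depends on counts they do not give. For multi-item QLQ-C30 scales the half-items rule in SAP 5.5 matters as well. On an assumed scale of three four-level items, a move between a score from two answered items (step 16.7) and one from all three (step 11.1) allows a change of 16.7 − 11.1 = 5.6 points, which the 5-point rule counts and the 10-point rule does not. Dropping the 5-point analysis for those scales would be unjustified.

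**Conclusion.** The point holds for two of the three primary PRO variables. For LC13 chest pain and cough the 5-point analysis must reproduce the 10-point analysis exactly, so the plan contains no working check of the threshold for them. This rests on the documents' single-item description, the 0-100 linear scoring, equally spaced levels, and an item format of at most 11 levels. It does not need the four-level assumption.

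For dyspnea the conclusion is conditional: identical if items × (levels − 1) is 10 or less, for example three four-level items, and potentially different with four. The consequence is one of interpretation. No PRO estimate is biased, and the primary DFS conclusion is untouched.

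**What to change.** In SAP 2.11:
- Keep the 5-point analysis for multi-item scales, including LC13 dyspnea and the multi-item QLQ-C30 scales.
- For LC13 chest pain and cough, and any other single-item scale, replace it with a worsening of more than one response category, that is, a change greater than 100/(k − 1) points.
- State that for single items the 5-point result equals the 10-point result by construction.
- State the item and level counts of the dyspnea scale, so that readers can tell whether its 5-point analysis is informative.

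The cost is a sentence or two of text and one threshold parameter in the existing program. The stricter rule yields fewer events and wider intervals. Subjects whose baseline is in the top two categories cannot have a score-based event in that analysis; those in the top category already cannot under the 10-point rule. The number of such subjects per arm should be reported beside the result.

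The close-out SAP shows that the primary analysis has already been reported. For outputs that exist, a footnote saying that the 5-point results for single items are identical by construction prevents the misreading. A stricter cut-off added now should be labelled post hoc.
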